# 岌 VHsquared

STATISTICAL ANALYSIS PLAN: PROTOCOL V56502 Page 16 of 40

For the endpoints CDAI score and PRO-2, the screening score will be considered as baseline.

Listings will include scheduled and unscheduled data.

### **6.3. DERIVED TIMEPOINTS**

Last observation carried forward (LOCF) method will be used for primary analysis. If any of the element (Patient reported data or Physician reported data or Haematocrit value ) of primary endpoint is missing at Day 42, LOCF will be applied and that element will be carried forward from last available post-baseline visit.

Also, LOCF will be performed as part of sensitivity analysis for the primary and secondary efficacy endpoints. The missing CDAI scores, CRP and FCP will be carried forward from the last available post-baseline measurements.

In addition, the worst observation carried forward (WOCF) will also be performed as part of sensitivity analysis for the missing CDAI scores, CRP and FCP from the available baseline, post-baseline and the unscheduled assessments.

The descriptive summaries of derived timepoints provided for the primary efficacy variables will be summarised and named as "Day 42 (LOCF)" and "Day 42 (WOCF)".

# 6.4. RETESTS, UNSCHEDULED VISITS AND EARLY TERMINATION DATA

For by-visit summaries, data recorded at the nominal visit will be presented. Last non-missing value for a particular parameter will be included in by-visit summaries and listings. as well where unscheduled measurements will also be considered.

Subjects who prematurely discontinue from the study for any reason, will be scheduled for an Early Termination (ET) visit, at which time all of the assessments listed for that visit will be performed.

In by-visit summaries of all study objectives the Day 42 or ET visit will be summarised as follows "Day 42/Early Termination".

Additionally, in by-visit summaries for primary efficacy variables CDAI score, CRP and FCP values "Day 42 (LOCF)" and "Day 42 (WOCF)" will also be summarised.

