### 4.2.6 Unscheduled Visits

Unscheduled visits, if needed, may occur at any time as deemed necessary by the Investigator or site staff. If a subject returns to the site for an unscheduled visit due to a safety reason, assessments indicated in should be performed. In addition, the Investigator may do other

safety assessments as deemed necessary. These assessments are not required for subjects who return to the site for administrative reasons (e.g., to pick up additional study drug).

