### 6.3.3 Electrocardiogram

Electrocardiograms will be evaluated at the time points indicated in . Electrocardiogram recordings will be obtained after the subject has been supine and at rest for at least five minutes. ECG results will be evaluated at the investigational site to monitor safety during the trial. The Investigator or designee will review, sign, and date each ECG reading. The Investigator or designee will determine if any abnormal results are of clinical significance. The ECG will be repeated if any results are considered by to be clinically significant.

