### 8.2.5.2 Safety Laboratory Tests

The results of safety laboratory tests will be summarised for each laboratory parameter and planned visit time point.

Continuous laboratory parameters will be summarised by visit time point using the number of subjects with non-missing data, mean, SD, median, minimum and maximum. Actual values as well as changes from Baseline will be summarised.

Categorical parameters will be summarised by the number and percentage of subjects within each category, relative to the total number of subjects in the SAF, with data available. In the event of missing test results, a "missing" category showing the number of subjects with missing test results at each level of summarisation will be presented.

Shift tables for specific time points versus baseline status will be presented for both continuous (categorised in accordance with study-specific reference ranges as Low, Normal, High) and categorical (using appropriate categories such as Normal, Abnormal) laboratory parameters. "Time point" in these tables may be either a specific visit, a final study visit or the entire study duration on-treatment.

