### 6.5. WINDOWING CONVENTIONS

No visit windowing will be performed for this study.

STATISTICAL ANALYSIS PLAN: PROTOCOL V56502 Page 17 of 40

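### SAP 6.4 gives two conflicting rules for the value shown in by-visit summaries; under one of them a repeat can displace the abnormal safety result that triggered it

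*SAP*

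**What the plan says.** SAP 6.4, which covers retests and unscheduled visits, opens with "For by-visit summaries, data recorded at the nominal visit will be presented". The next sentence is "Last non-missing value for a particular parameter will be included in by-visit summaries and listings", followed by a broken-off fragment: "as well where unscheduled measurements will also be considered". Neither statement is limited to efficacy or to safety data.

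SAP 6.5 adds "No visit windowing will be performed for this study". SAP 6.2 says "Listings will include scheduled and unscheduled data".

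For laboratory data, Protocol 8.2.5.2 states: "The results of safety laboratory tests will be summarised for each laboratory parameter and planned visit time point". It also plans shift tables against baseline, whose time point may be one visit, the final visit or the whole on-treatment period. Protocol 8.2.5.3 treats vital signs in a similar way and tabulates ECGs as normal or abnormal.

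The protocol foresees extra measurements of two kinds:

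- **Triggered by a result.** Protocol 6.3.3 says "The ECG will be repeated if any results are considered" clinically significant (the assessor is blacked out). Protocol 6.2.1 mentions repeating a laboratory test to confirm an abnormality.
- **Triggered by an event.** Protocol 4.2.6 requires assessments "If a subject returns to the site for an unscheduled visit due to a safety reason".

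**The concern.** The two sentences of SAP 6.4 agree only when a parameter has one value per visit. When there is a repeat, one sentence shows the scheduled result and the other shows the repeat. A programmer has to choose, and the SAP does not say which sentence governs.

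For safety data the choice is not neutral. An abnormal result is more likely to be repeated than a normal one. Under the last-value sentence, an abnormal Day 14 ECG or ALT that is normal on repeat could enter the Day 14 row as normal, while a normal Day 14 result would usually stay as it was. The table would then lose values because they were abnormal.

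This matters because Protocol 2.1 reports human dosing of at most 14 days before this trial, which doses for 42 days. After Day 1 there are two on-treatment visits (Days 14 and 42) and a follow-up at Day 56. SAP 4.1 plans no data monitoring committee. The by-visit tables are a main objective summary of laboratory and ECG safety, and they should not depend on an unstated choice.

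**Working it through.** The documents give no figure on this point, so there is nothing to reproduce. The check is a comparison of the texts, then arithmetic on assumed inputs to show how the size behaves.

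**1. The texts compared.**

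| Question | SAP 6.4, opening sentence | SAP 6.4, next sentence and fragment | Protocol 8.2.5.2 |
|---|---|---|---|
| Which value enters the visit row? | The nominal-visit value | The last non-missing value | Results by planned visit time point |
| Do unscheduled values count? | Not mentioned | They are considered | Not mentioned |
| How is an unscheduled value tied to a visit? | Not stated | Not stated; SAP 6.5 applies no windows | Not stated |

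The opening sentence fits the protocol and the next one does not. SAP 3.3, which records changes from the protocol, discusses only the model covariates and the response definition. A deliberate move away from planned time points is therefore not declared.

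**2. The shortfall if the last-value sentence is used.** Let *a* be the abnormal rate at the nominal visit, *r* the share of abnormal results that are repeated, and *q* the share of those repeats that are normal. Assume that normal results are not repeated and that the repeat falls in the same visit row. Then

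rate shown = a × (1 − r × q), and relative shortfall = r × q.

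The documents give none of *a*, *r* or *q*. Taking a = 10% as an assumption and 84 V565 subjects (Protocol 5.6), the scheduled count is 84 × 0.10 = 8.4.

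| r (assumed) | q (assumed) | r × q | Count shown: 8.4 × (1 − r × q) |
|---|---|---|---|
| 0 | any | 0% | 8.4 |
| 0.25 | 0.3 | 7.5% | 7.8 |
| 0.5 | 0.6 | 30% | 5.9 |
| 1 | 0.9 | 90% | 0.8 |

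**3. How large q could be by chance alone.** This was simulated with normally distributed values, a repeat whenever the value exceeds +1.96 SD, and no real recovery between the two measurements. The share of repeats back in range was 0.91, 0.82, 0.67 and 0.41 at within-subject correlations of 0.3, 0.5, 0.7 and 0.9. Regression to the mean alone can therefore make q substantial.

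**4. Effect on an arm comparison.** The model is the same, with every value above the cut repeated once (r = 1) and V565 assumed to shift the mean by 0.5 SD. Entries are percent above the cut.

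| Value used | V565 | Placebo | Difference (points) | Ratio |
|---|---|---|---|---|
| Scheduled | 7.21 | 2.49 | 4.72 | 2.9 |
| Last value, correlation 0.5 | 2.04 | 0.46 | 1.58 | 4.4 |
| Last value, correlation 0.7 | 3.11 | 0.83 | 2.28 | 3.7 |
| Last value, correlation 0.9 | 4.78 | 1.47 | 3.31 | 3.3 |

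The absolute difference falls by 1.41/4.72 = 30% to 3.14/4.72 = 67%. The ratio between arms rises. Both follow from r = 1, which no document supports.

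**The case against.** The strongest case on the other side is that this is a drafting slip in one sentence, with little consequence.

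- **The rule is not settled.** SAP 6.4 opens with the nominal-visit value, and the sentence after it is visibly broken. Read literally it would also confine listings to the last value, which SAP 6.2 contradicts. It might mean only the last value among records of the same visit. This stands, and it is why the finding is a conflict between two rules. The same-visit reading would still let a same-day ECG repeat displace the ECG that prompted it.
- **Abnormal results have other routes into the report.** Under Protocol 6.2.3 a laboratory abnormality judged clinically significant is an adverse event, and it reaches the TEAE tables if treatment-emergent. Protocol 8.2.5.3 lists clinically significant ECG abnormalities, and Protocol 8.2.5 lists all safety data by subject. This stands. These routes depend partly on the investigator's judgement, so they do not replace an objective table.
- **Direction.** A value from a symptom-driven safety visit can be worse than the scheduled one, so the last-value sentence could also raise abnormal counts. This stands for such values; the downward direction holds for repeats triggered by an abnormal result.
- **Missing text.** SAP 17.2.1 on markedly abnormal criteria appears in the contents list, but its body is not in this copy. Protocol 8.2.5.2 already commits to shift tables. It cannot be asserted that the plan lacks a table that keeps the abnormal value.
- **Stakes.** SAP 17 makes no statistical comparison between arms on safety data, so no test result is affected. This stands.

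A reader might infer that the trial's tables will understate toxicity, by some 30% to 67% of the arm difference. The documents do not support that. The governing rule is undecided, only by-visit summaries are exposed, and that range assumes every flagged value is repeated and refers to the absolute scale only.

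**Conclusion.** The point holds as an internal contradiction with a conditional consequence. SAP 6.4 gives two incompatible selection rules, and the visible text does not say how an unscheduled value is assigned to a visit. If the last-value sentence is applied to safety data, repeats triggered by abnormal results can replace those results in the by-visit laboratory, vital-sign and ECG tables. The abnormal counts shown then fall, contrary to the planned-time-point summaries in the protocol.

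The relative shortfall is r × q. It is zero if nothing is repeated and reaches 90% in the most extreme assumed case; the documents cannot place it within that range. TEAE and SAE tables are not built by this rule, and the listings keep every value. The matter is worth correcting because either reading of SAP 6.4 leads to the same simple repair.

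**What to change.** In SAP 6.4, replace the two sentences with one rule for by-visit laboratory, vital-sign and ECG summaries: use the scheduled result of the nominal visit, and use a repeat only if that result is missing or invalid. State how such a repeat is tied to its visit.

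In the shift tables already planned under Protocol 8.2.5.2, include a worst on-treatment category versus baseline that draws on all post-dose values, scheduled and unscheduled, unless SAP 17.2.1 already provides this. Unscheduled results then count in a table designed for them, whichever direction they go.

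The cost is SAP wording and a little programming, with no new data. The downside is small: some transient or spurious abnormal values will appear in the tables.

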#### 4.2.2 Treatment Period

During the treatment period, the subject will attend three site visits (Day 1, Day 14 and Day 42). If possible, site visits will be scheduled for the morning. The window for the Day 14 and Day 42 visits is -3 days to +1 day.

On Day 1, subject compliance with diary completion will be reviewed to confirm that diary compliance is still acceptable. If all eligibility requirements have been met (including those based on the results of the ileocolonoscopy), the subject will be randomised. If not, the subject will be considered a screen failure and the reason for the screen fail will be recorded.

Eligible subjects will be randomly assigned to receive one of two oral regimens: V565 555 mg TID or placebo.

The Day 1 assessments and procedures presented in will be completed prior to starting treatment with study drug. Treatment will begin on Day 1 at the site and continue to Day 42. Additional information on dosing is available in Section 5.8.

Subjects will continue to fill out their diaries daily throughout the treatment period. At each visit, site personnel will review the diaries and assess compliance with study drug administration and with the use of the diary.

Pharmacokinetic samples (blood and urine) will be collected at each study visit. On Day 1, subjects will be asked to provide a pre-treatment sample and an additional sample 4 to 8 hours after the first dose of study drug.

The subjects take their last dose of study drug on Day 42. The subjects will return to the site on Day 42 for the assessments and procedures indicated in . The subject diaries will be collected at this time. Subjects participating in the endoscopy substudy will have their second ileocolonoscopy performed on Day 42.

### 4.2.3 Follow-up: Day 56

The subject will return to the site for a follow-up visit at Day 56, approximately two weeks after the last dose of study drug. The procedures performed during the follow-up visit are presented in .

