### 4.2.5 Early Termination Visit

A subject will have an Early Termination Visit if they discontinue treatment with study drug or withdraw from the study. If a subject withdraws from the study, or is discontinued from treatment with study drug, every effort should be made to complete an Early Termination Visit with the same assessments as scheduled for Day 42. The Early Termination Visit should be scheduled as soon as possible after it has been decided that the subject will be permanently discontinued from treatment with study drug. In addition to the Early Termination Visit, the Follow-up Visit should be performed on Day 56 if possible. Details describing subject withdrawal are presented in Section 4.5.

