### 8.2.2 Secondary Efficacy Analyses

The secondary endpoints below will be analysed using the same model as used in the primary endpoint analysis.

- Proportion of subjects achieving a ≥100-point reduction in CDAI score and a concomitant reduction of 50% in CRP or FCP at Day 42
- Proportion of subjects achieving a  $\geq$ 70-point reduction in CDAI score at Day 42
- Proportion of subjects achieving a  $\geq$ 100-point reduction in CDAI score at Day 42
- Proportion of subjects achieving a CDAI score of <150 CDAI at Day 42

For the PRO-2 score assessments, the changes in total scores from Baseline to Day 14 and Day 42 will be analysed using a Mixed Model for Repeated Measures (MMRM) with treatment as the fixed effect, prior anti-TNF $\alpha$  and baseline scores as covariates.

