### 15.2.2. MISSING DATA METHODS FOR SECONDARY EFFICACY VARIABLE(S)

Imputation of secondary efficacy variables will also follow the same procedure as primary efficacy variables.

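### The 'Day 42/Early Termination' row can mix in values from any treatment day, and the SAP does not settle whether PRO-2 is carried forward before its repeated-measures model.

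*SAP*

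**What the plan says.** **Pooling of visits.** SAP 6.4 states: "In by-visit summaries of all study objectives the Day 42 or ET visit will be summarised as follows", followed by the combined label 'Day 42/Early Termination'. SAP 6.5 adds: "No visit windowing will be performed for this study". The visit labels in SAP Appendix 1 include that combined label, a Day 42 LOCF row and a Day 42 worst-observation row. None is for Day 42 alone or for ET alone.

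**Timing and content of ET.** Protocol 4.2.5 says: "The Early Termination Visit should be scheduled as soon as possible after it has been decided that the subject will be permanently discontinued". It also says "every effort should be made to complete an Early Termination Visit with the same assessments as scheduled for Day 42". For scheduled visits, Protocol 4.2.2 states: "The window for the Day 14 and Day 42 visits is -3 days to +1 day".

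**PRO-2.** The protocol makes change in PRO-2 at Day 14 and Day 42 a secondary endpoint, and Protocol 8.2.2 assigns it a mixed model for repeated measures (MMRM). SAP 15.2.2 states: "Imputation of secondary efficacy variables will also follow the same procedure as primary efficacy variables". The primary procedure is LOCF (SAP 6.3 and 15.1.2). SAP 6.3, however, describes LOCF for the secondary endpoints as part of the sensitivity analysis and names only CDAI, CRP and FCP as the measures carried forward.

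**PK and endoscopy.** SAP 16 summarises serum and urine V565 by visit. SAP 15.3.3.6 and 15.3.3.7 summarise mucosal appearance and SES-CD at Day 42.

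**The concern.** An ET visit can fall in any week of treatment, yet its values share a row with values taken after six weeks on drug. The combined label warns the reader that mixing may have occurred. It does not say how much, and no other planned row lets the two be separated. ET values also differ from Day 42 values in more than timing. Protocol 5.10.3 says that subjects should be withdrawn if they take prohibited medication or change background therapy, so an ET score may follow such a change. An ET sample for V565 may be taken after the last dose.

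For PRO-2 there is a second issue. After baseline it is measured only at Day 14 and at Day 42 or ET, so LOCF can only put a Day 14 or ET score into the Day 42 slot. A likelihood-based MMRM handles a missing Day 42 value through the observed Day 14 value without imputation. Filling the slot first tells the model that an earlier score is the six-week score. SAP 6.3 and 15.2.2 point different ways on whether this happens, so two programmers could produce different PRO-2 results from the same data.

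**Working it through.** **1. The plan's own figure.** The protocol synopsis gives 126 randomised (84:42), 10% dropout and about 114 completers (76:38). Check: 126 × 0.9 = 113.4; 84 × 0.9 = 75.6; 42 × 0.9 = 37.8. These agree with the stated figures after rounding.

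**2. Window.** Day 42 with −3 to +1 days is Days 39 to 43. Day 14 is Days 11 to 15. Nothing in SAP 6.4 or 6.5 limits ET records to either range.

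**3. Ceiling on non-Day-42 rows.** 84 − 76 = 8 and 42 − 38 = 4, so at most 12/126 = 9.5% overall, and likewise 8/84 and 4/42. This requires every dropout to attend ET, outside the window, with a usable value.

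**4. Dilution of a Day 42 difference.** Let s be the share of substituted values, equal in both arms, and f the fraction of the Day 42 effect that those values carry (f is an assumption). The expected difference is Δ × [1 − s(1 − f)], so the attenuation is s(1 − f).

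| s | f = 1 | f = 0.5 | f = 0 |
|---|---|---|---|
| 5% | 0% | 2.5% | 5% |
| 9.5% (planned) | 0% | 4.8% | 9.5% |
| 20% | 0% | 10% | 20% |

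**5. Simulation for PRO-2.** Assumptions, none of them from the documents: true effect −1 at Day 14 and −3 at Day 42, SD 7 to 8, dropout driven by poor Day 14 scores, 84:42, 4000 trials. At 8.3% dropout, maximum likelihood on observed data gives −2.99. Using the Day 14 or ET value as Day 42 gives −2.86, an attenuation of (3.00 − 2.86)/3.00 = 4.7%. The formula in step 4 with s = 0.083 and f = 1/3 gives 0.083 × 2/3 = 5.5%, which is consistent. At 16.7% dropout, with within-subject correlation 0.6, the two estimates are −2.98 and −2.73, an attenuation of 0.27/3.00 = 9%.

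**6. Unequal dropout.** Suppose there is no true effect, dropout is 5% in one arm and 15% in the other (assumed), and ET change is zero. The spurious difference is (15% − 5%) = 10% of the completers' mean change, with its sign set by which arm loses more subjects. In simulation with no true effect and unequal dropout, carry-forward gave a spurious difference of about 0.3 points, while observed-data likelihood stayed near zero.

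**7. Precision.** If carried values are counted as observed, at equal SD, the nominal standard error is √(1/84 + 1/42) ÷ √(1/76 + 1/38) = √(114/126) = 0.951 of the observed-data one, about 5% too small.

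Steps 5 and 7 bear on the model estimate only if carried or ET values actually enter the MMRM.

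**The case against.** The best case for the plan is that the pooling rule is confined to by-visit summaries and the row is openly labelled. A reader might infer that the MMRM also takes ET records as Day 42. No visible text says so.

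A reader might also conclude that the SAP definitely carries PRO-2 forward before the MMRM. The documents do not support that. The conclusion rests on one general sentence in SAP 15.2.2. SAP 6.3 points the other way, and SAP 15.1.2 speaks of imputing responder status, which PRO-2 does not have. The SAP's text on analysing the secondary variables and its MMRM code are not public, and that gap is no fault of the plan.

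The endoscopy and PK consequences are limited too. No post-baseline ileocolonoscopy precedes Day 42 or ET, so LOCF cannot affect endoscopy. Pooling matters there only if the ET visit includes the procedure, and the substudy is exploratory and not powered. For PK, the pharmacokineticist reviews affected data (SAP 5.4), sampling times are listed, and Phase 1 found no detectable V565 in serum (Protocol 2.1), so there may be no serum mean to dilute.

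All of this stands as narrowing. It does not remove the pooled row or the conflict between SAP 6.3 and 15.2.2. Time since stopping drug is also not among SAP 5.4's listed examples of events affecting PK data.

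**Conclusion.** The point holds in limited form, with minor to moderate weight. Day 42/ET summaries can include off-schedule and possibly off-drug values, and the planned tables give no way to separate them. The 9.5% in step 3 is a ceiling, not an expectation. Imputation of PRO-2 before the MMRM is an unresolved conflict within the SAP.

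Two stronger conclusions go too far. One is that the validity of the MMRM is lost: even if values are carried forward, the estimated distortion at planned dropout is about 5%, and that figure depends on assumed effects, SDs and dropout mechanism. The other is that the distortion is safely conservative: with unequal dropout it can favour either arm. Only secondary, exploratory and PK results are affected.

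**What to change.** 1. **SAP 6.4, 6.5 and Appendix 1.** Count an ET record as Day 14 or Day 42 only if its study day lies in that visit's protocol window and no scheduled-visit value exists. Show all other ET records in a separate 'Early Termination' row with study day and days since last dose.
2. **SAP 6.3 and 15.2.2.** State that the main PRO-2 MMRM uses observed Day 14 and Day 42 values without imputation, and that LOCF, including ET values, is a sensitivity analysis only.
3. **SAP 16.** Show ET samples for V565 in the ET row or a listing, with time since last dose. Admit them to the Day 42 summary only if they are in window and on treatment.

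The cost is SAP wording and one mapping rule based on recorded dates. The Day 42 row would hold about 114 subjects at planned dropout, where it might otherwise reach 126. Subjects who leave before the Day 14 window would contribute no post-baseline PRO-2 to the main MMRM. The LOCF sensitivity analysis would still use any ET value they have.
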